7.6 Pregnancy Reporting

Any pregnancy which comes to the attention of the Investigator during the study must be reported to the Sponsor and the IRB as soon as the Investigator or study staff becomes aware of the pregnancy. Subjects who become pregnant during the study will be required to discontinue treatment immediately and be discontinued from the study [REDACTED] Subject will be followed until completion of pregnancy. Pregnancy itself is not considered an AE/ADE. A congenital anomaly or birth defect will be reported as an SAE.

This figure is a 2D grayscale heatmap representing a probability density or a similar scalar field. The distribution is highly concentrated along the vertical axis, with a primary peak reaching the top of the plot. There are several smaller, secondary peaks along the vertical axis and a few distinct peaks along the horizontal axis. The distribution is rendered in black on a white background.

8.2 Potential Benefits

The subjects may or may not benefit from the study device. Potential benefit of laser treatment is reduction in number and/or severity of acne lesions. There is no guarantee of success.

9 RISK MANAGEMENT

Appropriate risk mitigation measures have been taken to support exposure of these patients to the investigational device, as described below.

The Investigators participating in this study will be chosen based on medical specialty, experience diagnosing and treating acne vulgaris, experience conducting clinical research studies and experience in the use of laser-based devices for aesthetic indications and/or dermatology applications.

In addition, all study Investigators (and qualified designees) will be trained on the use of the investigational Cutera® 1726 nm laser system by a representative of the Sponsor.

11 STATISTICAL CONSIDERATIONS

11.2 Reported Adverse Events

Adverse events (AE) will be categorized as serious and non-serious, device-related and non-device-related, and anticipated and unanticipated. All reported AEs should be followed until resolution. In the unusual circumstance that an AE has not resolved by the time of the subject's completion of the study, an explanation will be entered on the appropriate CRF.

11.3 Primary Effectiveness Endpoint – Percent Change from Baseline in Inflammatory Lesion Counts

Percent Change from Baseline in Inflammatory Lesion Counts (ILC) is calculated as:

$$\frac{100 \times (\text{Follow-Up Visit ILC} - \text{Baseline ILC})}{\text{Baseline ILC}}$$

such that a negative result reflects a decrease in the inflammatory lesion counts, while a positive result reflects an increase. A decrease in the inflammatory lesion counts indicates improvement, therefore negative values reflect improvement.

[REDACTED]

[REDACTED]
[REDACTED]

[REDACTED]
[REDACTED]

[REDACTED]

[REDACTED]
[REDACTED]

11.5 Primary and Secondary Safety Analyses

Overall safety of the Cutera® 1726 nm laser system for the treatment of mild to severe acne vulgaris will be assessed by a review of the totality of all reported adverse events.

[REDACTED]
[REDACTED]

| [REDACTED]
| [REDACTED]
| [REDACTED]

[REDACTED]
[REDACTED]

[REDACTED]
[REDACTED]

| [REDACTED]
| [REDACTED]
| [REDACTED]

[REDACTED]
[REDACTED]

[REDACTED]
[REDACTED]

[REDACTED]
[REDACTED]

[REDACTED]

[REDACTED]

[REDACTED]

[REDACTED]

[REDACTED]

[REDACTED]

11.8 Derived Data – Change-from-Baseline Parameters

Within-subject change-from-baseline (pre-treatment baseline) values for a parameter are calculated as:

$$\text{Change-from-Baseline} = \text{Follow-Up value} - \text{Pre-Treatment value}$$

such that a negative value indicates a reduction from the pre-treatment value to the follow-up value, whereas a positive result indicates the opposite.

[REDACTED]

[REDACTED]

[REDACTED]

[REDACTED]

11.10 Statistical Methods

Categorical data will be summarized using frequency tables, presenting the subject counts and relative percentages. McNemar's chi-square may be used to assess within-subject changes in a bivariate response variable.

Continuous variables will be summarized by the mean, standard deviation, median, minimum and maximum. Within-subject changes (Change-from-Baseline) will be analyzed parametrically using the

Paired t-test if the differences are normally distributed, or non-parametrically using the Sign-Rank Test if the differences are not normally distributed. Mid study evaluation of data may be performed to facilitate clinical study report writing. Investigators and panelists will remain blinded to such evaluation.

Appropriate statistical software will be used to perform all analyses. Exact confidence intervals will be generated for estimates of proportions. Asymptotic confidence intervals will be generated for estimates of means. Except where otherwise noted, the p-values of all tests will be reported without any correction for the multiplicity of tests performed.

The figure consists of a series of 10 horizontal bars, each composed of two black bars. The top bar in each pair is significantly thicker than the bottom one. The bars are arranged vertically. The second bar from the top has a small, irregular white rectangular gap in its center, while the other bars are solid black. The bars are set against a white background.

Confidential and Proprietary

Page 30 of 48

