4 STUDY DESIGN

This is a multi-center, prospective, open-label, single-arm study. Up to 15 study sites will enroll and initiate treatment on up to 107 male and female subjects, ages 16 to 60 years, who present with mild, moderate or severe facial acne at baseline, pass all eligibility criteria and desire laser treatment for their acne. Enrolled subjects will receive [REDACTED] laser treatments on the face [REDACTED]. Subjects will be followed at approximately 10 [REDACTED] days post each treatment (via phone) and at 4 [REDACTED], 12 [REDACTED] and 52 [REDACTED] weeks post-final treatment.

Subjects will be required to undergo a 1 month (30 day) washout period from topical retinoids and other systemic or topical acne medications prior to baseline, and for the duration of the study. If the acne medication is topical, the washout applies to use on the face only. [REDACTED]
[REDACTED]

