4.2 Study Outcome Measures - Effectiveness

4.2.1 Primary Endpoint

The primary outcome measure to evaluate the efficacy of the investigational Cutera® 1726 nm laser system for the treatment of mild to severe acne vulgaris is the percent reduction in inflammatory acne lesion count across the entire face (excluding areas not treated) for each subject from baseline to 12 weeks [REDACTED]

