5.1.1 Inclusion Criteria

To be included in the study, subjects must meet all of the following Inclusion Criteria:

1.	Female or Male, 16 to 60 years of age (inclusive).
2.	████████ Fitzpatrick Skin Type I-IV ¹⁹ ; ██████████ Fitzpatrick Skin Type V-VI ¹⁹
3.	Has clinically diagnosed acne vulgaris of severity grade 2 – 4 on the face ██████████ using the Investigator's Global Assessment Scale ██████████
4.	Has ██████████ inflammatory acne lesions on the face as determined by the Investigator (or qualified designee).
5.	Subject (and parent or legal guardian if subject is a minor under age 18) must be able to read, speak, and understand English and sign the Informed Consent Form.
6.	Willing to stop using topical retinoids and other acne medications for 1 month (30 days) prior to baseline and for the duration of the study. If the acne medication is topical, the washout applies to use on the face only.
7.	Willing and able to adhere to the treatment and follow-up schedule and pre/post-treatment care instructions.
8.	Willing to have very limited sun exposure (including avoiding tanning booths, sun lamps, sunbathing) and use an approved sunscreen of SPF 30 or higher on the face every day for the duration of the study, including the follow-up period.
9.	Willing to have photographs taken of the face and agree to the use of photographs for presentation, educational or marketing purposes.
10.	Agree to not undergo any other procedure(s) or add any new treatment modalities in the target area during the study.

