5.1.2 Exclusion Criteria

Subjects will be excluded from the study if they meet any of the following Exclusion Criteria:

1.	Has clinically diagnosed acne vulgaris of severity grade 0 or 1 on the face [REDACTED] using the Investigator's Global Assessment Scale.
2.	Prior treatment to the target area during participation in a clinical trial of another device or drug within 1 month (30 days) prior to study participation.
3.	Prior treatment to the target area within 3 months of study participation including chemical peel, dermabrasion, microneedling, radiofrequency treatment, laser or light-based procedures, cryodestruction or chemodestruction, intralesional steroids, photodynamic therapy, or acne surgery.
4.	Prior injection of botulinum toxin in the target area within 3 months of study participation and for the duration of the study.
5.	Prior injection of collagen, hyaluronic acid filler or other dermal filler in the target area within 6 weeks of study participation.
6.	Systemic use of retinoid, such as isotretinoin, within 6 months of study participation.
7.	History of malignant tumors in the target area.
8.	Excessive facial hair (e.g. beards, sideburns, moustaches, etc.) that would interfere with diagnosis or assessment of acne vulgaris in the target area (okay if shaved).
9.	Pregnant and/or breastfeeding or planning to become pregnant during the study.
10.	Presence of any skin condition in the target area (e.g. eczema, psoriasis, dermatitis, rash, papulo-pustular rosacea, infection) that would interfere with the diagnosis or assessment of acne vulgaris.
11.	Any medical condition that, in the opinion of the Investigator, would interfere with patient's participation in the full study protocol (e.g. severe Diabetes Mellitus or Cardiovascular Disease).
12.	Suffering from diagnosed coagulation disorders or taking prescription anticoagulation medications.
13.	History of diagnosed immunosuppression/immune deficiency disorders or currently using immunosuppressive medications.
14.	History of diagnosed connective tissue disease, such as systemic lupus erythematosus or scleroderma.
15.	Any use of medication that is known to increase sensitivity to light according to Investigator's discretion.
16.	History of disease stimulated by heat, such as recurrent herpes simplex and/or herpes zoster (shingles) in the target area, unless treatment is conducted following a prophylactic regimen.

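### Does naming McNemar's test in section 11.10 commit the trial to an IGA success test that a handful of responders would pass?

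*Combined protocol and SAP*

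**What the plan says.** The general methods paragraph of section 11.10 contains the only visible reference to the test: "McNemar's chi-square may be used to assess within-subject changes in a bivariate response variable". It names no endpoint, significance level, continuity correction or exact version. The same section adds "Exact confidence intervals will be generated for estimates of proportions" and, as a default that allows noted exceptions, "the p-values of all tests will be reported without any correction for the multiplicity of tests performed".

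The IGA scale is visible in two places, both about eligibility. Section 5.1.1, item 3, requires: "Has clinically diagnosed acne vulgaris of severity grade 2 – 4 on the face". Section 5.1.2, item 1, excludes a subject who meets: "Has clinically diagnosed acne vulgaris of severity grade 0 or 1 on the face".

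Section 4.2.1 gives the primary endpoint as "percent reduction in inflammatory acne lesion count across the entire face (excluding areas not treated) for each subject from baseline to 12 weeks", and section 11.3 gives its formula. Section 4 describes the design: "This is a multi-center, prospective, open-label, single-arm study". It caps enrolment at "up to 107 male and female subjects, ages 16 to 60 years".

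**The concern.** McNemar's test compares the number of subjects who gain a status with the number who lose it. Because the entry criteria remove grades 0 and 1, a success variable defined as IGA 0/1 is 0% at baseline by design. The loss cell is then empty by construction, and the uncorrected statistic is simply the count of responders. A responder defined by improvement from baseline behaves the same way.

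The null hypothesis then amounts to saying that nobody ever reaches success, and any spontaneous improvement makes that false. In a single-arm pivotal study meant to support a 510(k) submission, a p-value of this kind could be read as evidence of efficacy when it shows only that the response rate is above zero. By default it would also be reported without adjustment for multiplicity. The word bivariate, where binary is evidently meant, adds to the impression of a loosely written sentence.

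**Working it through.** There are two questions: whether the arithmetic is right, and whether the plan applies the test in this way. The plan states no figure on this point, so there is none to reproduce.

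**Arithmetic**

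Inputs:
- Up to 107 subjects (section 4). This is an enrolment cap, not an evaluable number.
- c = 0 losses, which follows from sections 5.1.1 and 5.1.2 if success means IGA 0/1.
- b = number of responders.
- Two-sided 0.05. This is an assumption, since no significance level is visible.

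Formulas with c = 0:
- Uncorrected: (b − c)²/(b + c) = b
- Continuity-corrected: (|b − c| − 1)²/(b + c) = (b − 1)²/b
- Exact, two-sided: p = 2 × 0.5^b

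| Responders b | Share of 107 | Uncorrected | Corrected | Exact | Exact 95% CI for b/107 |
|---|---|---|---|---|---|
| 4 | 3.7% | 4.00, p = 0.046 | 9/4 = 2.25, p = 0.134 | 0.125 | 1.0% to 9.3% |
| 5 | 4.7% | 5.00, p = 0.025 | 16/5 = 3.20, p = 0.074 | 0.0625 | 1.5% to 10.6% |
| 6 | 5.6% | 6.00, p = 0.014 | 25/6 = 4.17, p = 0.041 | 0.031 | 2.1% to 11.8% |

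The threshold is therefore 4 responders for the uncorrected statistic and 6 for the other two versions. With c = 0 it does not depend on the sample size.

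The chance of a significant result when the device does nothing is P(X ≥ threshold) for X binomial with 107 subjects and an assumed spontaneous response rate:

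| Assumed rate | Threshold 4 | Threshold 6 |
|---|---|---|
| 2% | 0.167 | 0.021 |
| 5% | 0.788 | 0.447 |
| 10% | 0.9955 | 0.963 |

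The documents give no spontaneous rate, and across this range the answer runs from 2% to nearly 100%. The arithmetic is correct, but its size depends on unstated inputs.

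**Does the plan do this?**

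- *Variable.* Sections 5.1.1 and 5.1.2 use IGA to select subjects. No visible text defines IGA success, a responder, or any other binary efficacy endpoint.
- *Link.* Section 11.10 attaches McNemar's test to no named variable and makes it optional.
- *Visible endpoint.* Sections 4.2.1 and 11.3 define a continuous percent change. McNemar's test cannot be applied to it. For within-subject changes in continuous variables, section 11.10 provides the paired t-test or the signed-rank test.
- *Unseen text.* The visible headings go from 4.3 to 4.5, from 11.3 to 11.5, from 11.5 to 11.8 and from 11.8 to 11.10, and much of 11.5 is blacked out. Secondary endpoints and their tests could be defined there. Blacked-out text cannot be treated as absent from the plan.
- *Safeguard.* The exact interval for proportions is already planned. For 4 of 107 it would read 1.0% to 9.3%, which shows plainly how weak such a result is.

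**The case for a change.** The strongest reply is that the sentence carries no restriction. IGA is the only graded acne scale visible, so IGA success is a natural candidate for a binary analysis. An optional method leaves the misuse open, and a one-sentence restriction would cost almost nothing in a pivotal study.

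Part of this stands. If the test were applied to IGA 0/1, its p-value would add almost nothing to the response proportion, and a reader of the eventual report should give it no weight as evidence of a device effect. That is a conditional caution about reporting. It does not show that the plan contains the error, because the step from an eligibility scale to a tested endpoint is an inference.

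The wider worry, that natural course and regression to the mean cannot be separated from a device effect, also stands, but it belongs to the design. Any before-after test in a single-arm study has that limit, including a paired t-test on lesion counts. Restricting McNemar's test would not remove it.

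The proposed replacement, a week-12 proportion with an exact interval, relies on an interval that section 11.10 already provides. A reference rate would be needed only if a formal test were wanted, and no visible text calls for one.

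**Conclusion.** The concern does not hold. Section 11.10 permits a standard test for paired binary data, and no visible text applies it to a variable whose baseline value is fixed by eligibility. The thresholds of 4 responders (uncorrected) and 6 (corrected or exact) of 107 are correct. They rest on three assumptions that the visible documents do not supply: an IGA 0/1 or similar success endpoint, the use of McNemar's test on it, and a two-sided 0.05 level. The false-positive figures also need an assumed spontaneous response rate.

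The effect on any visible analysis is nil: the primary endpoint is continuous, and exact intervals for proportions are already planned. The word bivariate is a slip for binary with no analytic consequence. This conclusion is limited to the visible text. If the unredacted plan did assign McNemar's test to IGA success, the calculation above would apply to it.

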4.7 Study Discontinuation

The Investigator and/or the Sponsor has the right to terminate this study at any time. Reasons for terminating the study may include, but are not limited to, the following: incidence or severity of adverse events in this or other studies indicates a potential health hazard to subjects; subject enrollment is unsatisfactory; number of protocol deviations is unacceptable; data recording is inaccurate or incomplete; or questionable study site compliance with Good Clinical Practice, FDA 21 CFR Part 812 and other applicable regulations.

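### Does the optional mid-study evaluation of data leave the primary p-value unprotected?

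*Combined protocol and SAP*

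**What the plan says.** The provision is in Section 11.10 (Statistical Methods): "Mid study evaluation of data may be performed to facilitate clinical study report writing". The next sentence adds "Investigators and panelists will remain blinded to such evaluation". The same section sets the default for multiplicity: "Except where otherwise noted, the p-values of all tests will be reported without any correction for the multiplicity of tests performed".

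Three other places bear on the point:

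- Section 4 (Study Design) fixes the size: "Up to 15 study sites will enroll and initiate treatment on up to 107 male and female subjects". It describes an open-label, single-arm study with follow-up at 4, 12 and 52 weeks after the final treatment.
- Section 4.2.1 defines the primary endpoint as the "percent reduction in inflammatory acne lesion count across the entire face (excluding areas not treated) for each subject from baseline to 12 weeks".
- Section 4.7 (Study Discontinuation) states that "The Investigator and/or the Sponsor has the right to terminate this study at any time" and introduces its list with "Reasons for terminating the study may include, but are not limited to, the following". The listed reasons are safety, unsatisfactory enrolment, protocol deviations, data quality and site compliance.

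In the public copy, Section 11.3 (Primary Effectiveness Endpoint) is blacked out after the percent-change formula. Sections 11.1, 11.4, 11.6, 11.7 and 11.9 cannot be seen.

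**The concern.** Section 1 calls the study pivotal and says that it is meant to support a 510(k) submission. The visible sentence on mid-study evaluation does not say how many evaluations there may be, when they occur, which endpoints they cover, or that the results cannot influence enrolment or termination. The people kept blind are those who treat and assess. The sponsor, who decides whether to stop, is not named. A study report normally carries the effectiveness result, so report writing describes a use of the data more than it limits that use.

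With uncorrected p-values, no visible minimum sample size and a broad right to terminate, one can imagine a sponsor testing a partial cohort, stopping if the result is favourable and continuing if it is not. The nominal level of the primary test would then be exceeded, and an estimate reported at an early favourable look would be too large. Blinding the assessors would prevent neither.

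**Working it through.** **Inputs.** The maximum of 107 subjects (Section 4), the primary time point of week 12 (Section 4.2.1), the last follow-up at week 52 (Section 4) and the paired t-test or signed-rank test (Section 11.10) come from the plan. The significance level is not visible, so two-sided 0.05 is an assumption. The number and timing of looks, and the right to claim success at each, are also assumptions. The figure of 107 cannot be reproduced because its inputs are not visible.

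**Step 1: type I error under the feared use.** Let look *i* occur at information fraction t_i. The test statistics are jointly normal with correlation √(t_i/t_j) for t_i < t_j. Testing each at |Z| > 1.96 gives

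overall error = 1 − P(|Z_1| < 1.96, …, |Z_k| < 1.96).

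For looks at 50% and 100% the correlation is √0.5 = 0.707 and the error is 0.083. A simulation of 100,000 one-sample t-tests at n = 54 and then n = 107 also gave 0.083, with 0.049 for the final test alone.

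| Looks (fraction of information) | Overall two-sided error |
|---|---|
| 100% only | 0.050 |
| 90%, 100% | 0.065 |
| 75%, 100% | 0.073 |
| 50%, 100% | 0.083 |
| 25%, 100% | 0.091 |
| three, equally spaced | 0.107 |
| four, equally spaced | 0.126 |
| five, equally spaced | 0.142 |

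**Step 2: bias of the estimate under the same use.** Assume an SD of 40 percentage points, looks at n = 54 and n = 107, and stopping at the first if p < 0.05. The SD and the true effects are illustrative and are not in the plan.

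| True mean change | Average reported change |
|---|---|
| −10% | −11.0% |
| −20% | −20.2% |
| −30% | −30.0% |

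At a true −10%, a little over 43% of trials stop early, and those report −14.8% on average. At −30% nearly every trial stops at the first look, so there is almost no selection and almost no bias.

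**Step 3: does the plan provide for that use?** Every row of the first table below the first needs a success claim, or a stop, at an early uncorrected look.

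- *Purpose.* Section 11.10 names report writing only. It mentions no claim, stopping or change of sample size.
- *Termination.* No reason listed in Section 4.7 is efficacy. The list is not exhaustive, but stopping for safety or conduct does not by itself inflate the type I error.
- *Sample size.* 107 is a fixed ceiling. Going above it would need an amendment with IRB and FDA approval (Section 12.4.1). Only the lower end is open in the visible text.
- *Multiplicity.* The no-correction sentence opens with an exception clause and concerns the number of tests performed. It does not say that repeated looks at the primary endpoint go uncorrected.

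**Step 4: a reading that fits.** The primary endpoint is complete at week 12 and follow-up runs to week 52, so 52 − 12 = 40 weeks remain after each subject's primary visit. A report on the complete 12-week data, written while those 40 weeks run, is a mid-study evaluation for report writing. It is a single test on the full cohort, and the error stays at 0.05.

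**The case for a change.** The strongest reply is that the permissive sentence is itself fully visible. It carries no exception clause of its own and points to no controlling section, so blacked-out text elsewhere does not settle the matter. The 12-week reading is an inference, since nothing visible ties the evaluation to completion of the primary visit. The study is open-label with one arm, so accumulating data are easy to interpret. If an early report were the one submitted, the relevant bias is that among trials that stop: −14.8% against a true −10%, an overstatement of nearly half. One sentence in the plan would close the question at almost no cost.

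Part of this stands. The visible text leaves unstated the timing of the evaluation, the endpoints it covers, the sponsor's access, and that it drives no decision. The arithmetic is also right. But both the inflation and the bias need a decision rule that the plan does not contain, and the −14.8% depends on a weak assumed effect and on selecting the trials that stopped. The added sentence would record what a statistician would do anyway. It would not alter a sound analysis.

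**Conclusion.** No change follows. The gap is one of missing detail about an optional evaluation whose only stated purpose is report writing. A sponsor who follows the visible plan, and evaluates the primary endpoint once all 12-week data are in, obtains a valid primary test with no inflation.

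Errors of 0.065 to 0.142 arise only with one to four unadjusted interim tests plus the final, each at an assumed two-sided 0.05 and each able to support a claim. The plan sets out no such procedure. Nor can it be concluded that the primary p-value lacks protection, because the hypothesis, significance level and success criterion that would settle this are not visible in the public copy.

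The conclusion rests on taking the stated purpose at face value. It would change if the sponsor had in fact tested a partial cohort and used the result to claim success or to end enrolment. That would be a question about conduct, and the dates of the data cut and of the end of enrolment would answer it.
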